1.5 Randomization

After enrollment has been completed, subjects will be randomized (3:2 ratio) to either the SCS arm or the CMM arm at each site.

- Comprehensive Medical Management (CMM arm)

During the follow-up period, subjects in the CMM arm will receive supervised medical care, including medication optimization and supervised non-interventional therapy. Medication optimization should include use of non-steroidal anti-inflammatories and muscle relaxants, as appropriate. Supervised non-interventional therapy may include, but is not limited to, physical therapy, chiropractic care, back school, cognitive behavioral therapy, and acupuncture. Interventional therapy such as injections and radiofrequency ablation, is also allowed.

- Spinal Cord Stimulation (SCS arm)

A successful trial, defined as $\geq 50\%$ decrease in back pain recorded on Numerical Rating Scale, is required for a subject to receive a permanent implant.

1.6 Blinding

For this study, the subject, site personnel, and some sponsor personnel will be aware of treatment assignment. Sponsor statisticians, including the DISTINCT Study Statistician, will not have access to any data that combines outcomes with treatment assignment prior to performing the primary endpoint analysis of the randomized cohort.

Statistical Analysis Plan

2.0 ANALYSIS CONSIDERATIONS

2.1 Analysis Populations

The analysis populations include:

1. Intention-to-Treat (ITT) Population: includes all randomized subjects. Subjects will be analyzed according to the treatment group they are randomized to. The ITT population will be used as the primary analysis population for the primary endpoint.
2. Modified Intention-to-Treat (mITT) Population: includes all randomized subjects except for those who are randomized to the SCS group who fail the trial period, do not receive a permanent system implant. Subjects will be analyzed according to the treatment group they are randomized to.
3. Per-Treatment Evaluable (PTE) Population: includes all subjects in the mITT population who either receive permanent implant or receive CMM. Subjects will be analyzed according to the actual treatment received. The PTE population will be used as the primary analysis population for the study except the primary endpoint analysis.

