6.5.2 Trial Period

Subjects randomized to receive spinal cord stimulation will first undergo a trial of the therapy. The trial period implementation should start no more than [REDACTED] days after the Baseline visit and should last at least 4 days. Only percutaneous leads may be used for the trial procedure. "On the table" trials and the use of paddle leads for the trial procedure are not allowed.

The following data will be recorded at trial implementation:

- Trial system details
- Device programming
- Device- and/or procedure related adverse events (if applicable)
- All serious adverse events (if applicable)
- Withdrawal (if applicable)

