2.4 Sample Size/Power Calculations

The study was designed to enroll approximately 200 subjects in Phase I and up to 70 subjects in Phase II. The following assumptions are used in the power calculation for the primary endpoint:

- Assumed response rate of 45% for the SCS group and 20% for the CMM group
- 3:2 (SCS:CMM) randomization ratio
- 25% attrition rate to primary endpoint (6 months) follow-up in both groups
- Two-sided alpha of 0.05
- Z-test with unequal variance

Based on the assumptions above, there is at least 90% power to evaluate the primary endpoint with the Phase I cohort.

The minimum detectable differences for secondary endpoints using phase I PTE cohort (assume approximately 80 SCS and 60 CMM) with 80% power are shown in Table 1 below.

Table 1: Minimum Detectable Differences (MID) for Secondary Endpoints

Secondary Endpoints	MID (standard deviation for each group)
#1: Composite Responder	23%
#2: Relative NRS Change in %	16.9(35)
#3: ODI Change	7.2 (15)
#4: PCS Responder	21%
#5: PGIC (%)	23%
#6: Relative Pain Interference Change in %	7.2 (15)
#7: Relative Physical Function Change in %	12.0 (25)

The sample size re-estimation will be based on the interim analysis (IA) population (Adaptive Design Plan CL1014964). The unblinded independent statistician will perform the sample size re-estimation for 4 endpoints (1 primary and secondary endpoints #1, #2, and #3) and generate a recommendation if more subjects are needed to meet the statistical significance of each endpoint.

The power calculation was performed using PASS 15 (NCSS LLC).⁵

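### Secondary endpoints #1–#7 are tested in the type I error hierarchy on a population that drops SCS trial failures, and the visible SAP plans no as-randomised analysis of them

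*SAP*

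**What the plan says.** **Order of events.** Protocol 6.5.2: "Subjects randomized to receive spinal cord stimulation will first undergo a trial of the therapy". Randomisation comes first (Protocol 6.3). SAP 1.5 requires at least a 50% fall in back pain NRS in the trial before a permanent implant.

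**Populations (SAP 2.1).** ITT is primary for the primary endpoint only. For the rest: "The PTE population will be used as the primary analysis population for the study except the primary endpoint analysis". The mITT set omits SCS-randomised subjects "who fail the trial period, do not receive a permanent system implant". PTE is a subset of it and "includes all subjects in the mITT population who either receive permanent implant or receive CMM". On grouping: "Subjects will be analyzed according to the actual treatment received".

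**Secondaries.** SAP 2.3.2 names no other population. SAP 2.4 confirms PTE: "The minimum detectable differences for secondary endpoints using phase I PTE cohort" are computed with the sizes "assume approximately 80 SCS and 60 CMM". SAP 2.11 tests #1–#7 in fixed order at two-sided 5% to control type I error, after SCS superiority on the primary. SAP 2.6 mentions ITT alongside the secondaries, but only to set the timing of analysis.

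**Primary.** Trial failures stay in as non-responders (SAP 2.3.1.1). Multiple imputation and the mITT and PTE re-analyses (SAP 2.3.1.2, 2.9) concern the primary alone, and SAP 2.12 limits sensitivity analysis to it.

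**The concern.** Membership of PTE depends on a pain response measured after randomisation, in one arm only. SCS subjects who respond poorly to the trial leave the comparison; comparable CMM subjects stay. The same NRS scale defines #2 and is one component of #1. The SAP avoids this problem for the primary by keeping trial failures in as non-responders, and then admits it for every secondary.

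At stake is what a secondary result can be said to show. A result reported as passing a controlled hierarchy would be read as a randomised comparison. On PTE it is not one, and the visible plan gives no as-randomised result beside it.

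**Working it through.** **Inputs (SAP 2.4).** 200 subjects in Phase I; 3:2 allocation; response rates 45% and 20%; "25% attrition rate to primary endpoint (6 months) follow-up in both groups"; PTE about 80 SCS and 60 CMM; SDs 35, 15 and 25.

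**1. The plan's own figures.** Evaluable subjects: SCS 200 × 3/5 × 0.75 = 90; CMM 200 × 2/5 × 0.75 = 60. Primary power, unpooled Z: Φ(0.25/√(0.45×0.55/90 + 0.20×0.80/60) − 1.96) = Φ(3.397 − 1.96) = 92.5%; exact binomial enumeration gives 91.5%. This agrees with the stated minimum of 90%. Noncentral-t detectable differences at 80/60 for SDs 35, 15 and 25 are 16.86, 7.23 and 12.05, against 16.9, 7.2 and 12.0 in Table 1.

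**2. Size of the exclusion.** The PTE count for CMM equals the evaluable 60, but for SCS it is 80 against 90. If the gap is trial failures (an inference), f = 10/90 = 11%. Reading the approximate 80 as 75–85 gives f = 5.6–16.7%.

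**3. The gate.** Exact enumeration, unpooled Z, 90 v 60. With equal true rates of 20–50% it opens for SCS 2.7–3.0% of the time. At 45% v 20% it opens 91.5% of the time.

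**4. A binary secondary with no true effect.** True rate p in both arms. The SCS rate in PTE becomes p/(1−f) if all those removed are non-responders, p(1−f/2)/(1−f) if they respond at half the average rate, and stays p if unrelated. With f = 1/9 and all removed non-responders, 20% reads 22.5% and 50% reads 56.25%. Chance of a false SCS-favouring result (pooled chi-square, exact enumeration, nominal 2.5%, p from 20% to 50%):

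| SCS removed | All non-responders | Half rate | Unrelated |
|---|---|---|---|
| 5.6% (85 v 60) | 3.4–5.4% | 2.8–3.7% | 2.3–2.5% |
| 11% (80 v 60) | 5.3–10.9% | 3.7–5.5% | about 2.4% |
| 16.7% (75 v 60) | 7.9–21.4% | 4.6–8.6% | 2.4–2.6% |

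These rates are ungated and serve as the bound, because passing the gate as well cannot be more likely than the false positive alone.

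**5. Relative NRS change (#2).** Here the main risk is an inflated estimate. If the lowest f of trial scores are removed and trial score correlates ρ with the outcome, the SCS mean shifts by ρ × 35 × φ(c)/(1−f), with c the f-quantile. At f = 1/9 this is 2.2, 3.7 or 5.2 points for ρ = 0.3, 0.5 or 0.7 (assumed), and zero for ρ = 0.

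**6. Offset from CMM.** If 5.6% of CMM leave and all are non-responders, the 5.3–10.9% falls to 3.7–5.8%. If 11% do, it is 2.4–2.5%.

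**7. Rules for trial failures in an ITT analysis** (11% failing, p from 20% to 50%). Counting them as non-responders gives 2.2–2.7% in each direction if they truly are, but a CMM-favouring error of 5.7–9.2% if trial result and outcome are unrelated. Imputing from CMM (simulation, 50 imputations) gives 1.5–2.1% SCS-favouring and 1.2–1.5% CMM-favouring if unrelated; the SCS-favouring error is 3.0–3.4% at half rate and 4.5–7.3% if all are non-responders. Neither rule is neutral in every case.

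**8. Power for #2 under ITT.** If failures resemble CMM, 16.9 × 80/90 = 15.0 points. At 90/60 and SD 35 power is about 72%, against 80% in PTE.

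**The case against.** The strongest defence is that nothing decisive rests on the secondaries. Success is defined by the ITT primary (SAP 2.7), and SAP 2.11 blocks every secondary claim if that fails. This stands, and it keeps the point below the level of study validity. It does not protect the size of a secondary estimate, or a null secondary, once the primary has succeeded.

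The failure rate is not stated, and the error is nominal if trial result and outcome are unrelated or if CMM loses non-responders equally. Both points stand, which is why the figures are conditional. PTE also answers a fair question about implanted subjects and can be kept as a supportive analysis.

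Three stronger readings are tempting, but the documents do not support them:

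- **No as-randomised analysis exists anywhere.** Protocol 8.1 is redacted, 8.2.2 is partly redacted, and the Adaptive Design Plan, which details the final tests of #1–#3 if the sample size is increased, was not supplied. The statement holds only for the visible SAP.
- **Treatment-received grouping, or the unclear mITT wording, moves many subjects between arms.** The clause "who fail the trial period, do not receive a permanent system implant" has no connector, so those who pass the trial but decline the implant are not clearly placed. But Protocol 6.6.4 bars crossover before the 6-month visit and has unwilling subjects withdrawn. PTE also requires an implant or CMM. The effect on 6-month secondaries should be small.
- **Multiplying the step 4 rates by 0.915 gives an upper bound.** It does not when primary and secondary are correlated. At a true rate of 40% and latent correlation 0.7, simulation gave a joint rate of about 8.5%, against about 7.7% under independence.

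**Conclusion.** The concern holds as a should-fix on the one-sided exclusion. In the visible SAP, #1–#7 are tested under type I error control on PTE, without the SCS subjects who fail a post-randomisation trial judged on NRS, and with no as-randomised counterpart. The bias towards SCS is likely for #1 and #2, which use NRS. It is uncertain for #3–#7, and absent for any endpoint that trial response does not predict.

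The size can only be illustrated. It rests on the inferred 11% removed, on how those removed would have fared at 6 months, and on CMM not losing non-responders in the same proportion. The finding about the populations depends on none of these. A reader might infer that the trial's headline conclusion is compromised; SAP 2.7 rules that out.

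**What to change.** **Population.** In SAP 2.1, 2.3.2 and 2.11, pre-specify an as-randomised (ITT) analysis of #1–#7, preferably as the confirmatory one. At minimum, report it beside PTE for every secondary. Label PTE and mITT results as non-randomised comparisons.

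**Trial failures.** For the NRS component of #1, count them as non-responders, as the primary does. Do not make them failures on the ODI component automatically. For that component and #2–#7:

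- Use any 6-month or final-visit patient-reported data collected. Protocol 5.6 asks sites to attempt a final visit when consent is withdrawn; whether that covers trial failures is not stated.
- Let the end-of-trial NRS (Protocol 6.5.3) inform imputation.
- Otherwise pre-specify one rule, for example imputation from CMM, with non-response or zero change as sensitivity, and report both (step 7).

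**If ITT becomes confirmatory.** Restate Table 1 for about 90/60. With SDs unchanged the detectable differences for SDs 35, 15 and 25 are 16.45, 7.05 and 11.75, before allowing for the dilution in step 8. Align the re-estimation and CHW tests of #1–#3 in the Adaptive Design Plan.

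**Minor.** Reword the mITT clause to say where subjects who pass but decline the implant belong.

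**Cost.** Text changes only; no new data. Secondary effects will look smaller and power falls: for #2 to about 72% with imputation from CMM. Under zero change the #2 difference is 15.0 − m/9, where m is the CMM mean: 13.9, 12.8 or 11.7 points at assumed m of 10, 20 or 30, with simulated power of 67%, 59% or 50%.

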2.2 Statistical Methods

2.2.1 Analysis of Continuous Data

For continuous variables (e.g., age, etc.), results will be summarized as number of observations, means, and standard deviations, and where applicable, with quartiles, minimums, maximums, and 95% confidence intervals for the means. Difference between two groups, when specified, will be summarized with difference of the two means, and the 95% confidence interval of the differences. The p-values will be calculated based on either two-sample t-test or Wilcoxon rank sum test as appropriate.

Cumulative distribution function (CDF) may be used in displaying a continuous plot of the percent change from baseline on the horizontal axis and the cumulative percent of patients experiencing up to that change on the vertical axis. Kolmogorov-Smirnov test may be used to test whether two empirical distributions are different using proc npar1way in SAS®¹.

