8.2.2 Secondary Endpoint(s) Analyses

Selected secondary endpoints (e.g., composite responder rate based on NRS or ODI improvements, change on ODI from baseline, % change in NRS from baseline) will be compared between the two treatment groups. Appropriate statistical methods will be used according to the types of the data. Continuous variables may be analyzed using the [REDACTED]. Binary variables may be analyzed using tests such as [REDACTED]. Further details are described in the Statistical Analysis Plan (SAP).

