2.2.2 Analysis of Categorical Data

For categorial variables (e.g. gender, etc.), results will be summarized with subject counts and percentages/rates, and where applicable, with exact 95% Clopper-Pearson² confidence intervals. The p-values will be based on either Pearson's Chi-square test or Fisher's exact test by checking the expected frequency for each cell in the maximum contingency table against Cochran's rule³ (i.e. if the expected frequencies for all cells are ≥ 5 , then Pearson's Chi-square test will be used, otherwise Fisher's exact test will be used).

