2.2.4.2 Mixed effects model

For repeated measured variables, such as responder rate, patient report outcomes (PROs) at each visit, mixed effects models may be used to conduct exploratory analyses to evaluate the difference between SCS and CMM. Data can be analyzed using proc mixed for continuous variables or proc glimmix for binary variables from SAS®. Models will be compared and selected using likelihood ratio test, AIC or BIC.

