2.5 Interim Analysis

Interim analysis for sample size re-estimation will be considered to determine the sample size and the timing of primary analysis. There is one planned interim analysis which will be conducted when 70% of the Phase I randomized subjects reach/or complete the 6-month visit. If the sample size is increased, the CHW weighted statistic⁶ will be used in the final analysis of the primary and secondary endpoints 1, 2, and 3. Details are be shown in Adaptive Design Plan CL1014964. .

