2.11 Multiplicity Issues

To control for type I error inflation, the test of secondary endpoints will be performed in a hierarchical order at two-sided 5% significance level:

1. Secondary endpoint #1
2. Secondary endpoint #2
3. Secondary endpoint #3
4. Secondary endpoint #4
5. Secondary endpoint #5
6. Secondary endpoint #6
7. Secondary endpoint #7

The secondary endpoints will be tested only if the superiority in the SCS group is demonstrated in the primary endpoint. If hypothesis testing for superiority of secondary endpoint #1 fails, no hypothesis testing for the rest of secondary endpoints, etc.

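### SAP 2.2.1 leaves the test for the gatekept continuous secondaries (#2, #3, #6, #7) open between t-test and Wilcoxon and uses no baseline covariate; name one baseline-adjusted ANCOVA before the interim analysis

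*SAP*

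**What the plan says.** For continuous variables, SAP 2.2.1 states: "The p-values will be calculated based on either two-sample t-test or Wilcoxon rank sum test as appropriate". It does not say what makes one or the other appropriate, or whether the t-test is pooled or Welch. The same section fixes the effect measure: "Difference between two groups, when specified, will be summarized with difference of the two means", with a 95% confidence interval.

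SAP 2.3.2.2, 2.3.2.3, 2.3.2.6 and 2.3.2.7 define #2 (percent change in NRS), #3 (change in ODI), #6 and #7 (percent change in two PROMIS-29 domains) and state hypotheses, but name no test. All four belong to the sequence in SAP 2.11: "the test of secondary endpoints will be performed in a hierarchical order at two-sided 5% significance level". A failed step ends testing.

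Elsewhere the SAP is specific. The primary endpoint has one named test (2.3.1.1). For categorical data, SAP 2.2.2 chooses between chi-square and Fisher "by checking the expected frequency for each cell in the maximum contingency table".

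Baseline NRS, ODI and PROMIS-29 are collected (Protocol 6.2.2). Adjusted logistic regression is optional and for binary variables (SAP 2.2.4.1). For repeated measures, "mixed effects models may be used to conduct exploratory analyses to evaluate the difference between SCS and CMM" (SAP 2.2.4.2). No confirmatory test of a continuous endpoint has a baseline covariate.

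**The concern.** A non-significant result at #2 or #3 closes every later test, so the choice between two tests can decide which endpoints are tested at all. The secondaries are analysed together with the primary (SAP 2.6). That is when the SAP 1.6 restriction on sponsor statisticians seeing outcomes by arm ends, so a choice made then is not protected by the text. A Wilcoxon p-value also need not agree with the mean-difference interval that will be printed beside it.

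For #2 and #3 the matter arises earlier. "The unblinded independent statistician will perform the sample size re-estimation for 4 endpoints", the primary and #1 to #3 (SAP 2.4). If the sample size is raised, the CHW weighted statistic "will be used in the final analysis of the primary and secondary endpoints 1, 2, and 3" (SAP 2.5). Both steps need a defined test.

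Separately, a change-score test without the baseline covariate can give away precision at no saving, since the baseline is already measured.

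**Working it through.** **Inputs.** From SAP 2.4 and Table 1: 80 SCS and 60 CMM in the PTE cohort, 80% power, SDs 35 (#2), 15 (#3), 15 (#6) and 25 (#7). From SAP 2.11: two-sided 5%. Not in the documents, hence assumed: the distribution shape, the baseline to 6-month correlation ρ, and k = baseline SD / 6-month SD.

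**1. Table 1 reproduces as a t-test.** The standard error is SD × √(1/80 + 1/60) = 0.1708 × SD. The normal approximation, 2.80 × 0.1708 × SD, gives 16.75, 7.18 and 11.96 for SDs 35, 15 and 25. The noncentral t with 138 df gives 16.86, 7.23 and 12.05; Table 1 states 16.9, 7.2 and 12.0. A Wilcoxon test on normal data would need these divided by √(3/π) = 0.977, that is 17.3, 7.4 and 12.3. The planning therefore presupposes the t-test that SAP 2.2.1 leaves optional.

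**2. What the open choice can do.** Simulation at 80/60, SD 15, with normal data or lognormal data of assumed skew 1.8:

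| | Normal | Skew 1.8 |
|---|---|---|
| Size of each test alone | about 0.05 | about 0.05 |
| Size if the smaller p-value is always taken | about 0.06 | 0.069 |
| Tests disagree at a true difference of 7.23 | about 5% | about 13% |
| Wilcoxon significant, mean-difference interval covers 0 | 1.7% | 13.0% |

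A normality rule fixed in advance held the size at 0.051. What does the damage is the missing rule, not the offer of two tests.

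**3. Pooled or Welch.** With assumed SDs of 12 (SCS) and 18 (CMM), the size is 0.067 for the pooled t-test, 0.053 for Welch and 0.051 for ANCOVA with robust (HC3) errors.

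**4. Gain from the covariate, #3.** The detectable difference is multiplied by √[(1 − ρ²)/(1 + k² − 2ρk)]. For ρ = 0.5 and k = 1 this is √(0.75/1) = 0.866, and 7.23 × 0.866 = 6.3.

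| k | ρ = 0.3 | ρ = 0.5 | ρ = 0.7 |
|---|---|---|---|
| 1 | 5.8 | 6.3 | 6.7 |
| 0.85 | 6.3 | 6.7 | 7.1 |
| 0.7 | 6.7 | 7.0 | 7.2 |

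Entry requires ODI of at least 30% (Protocol 5.3.2), which truncates the baseline distribution. So k below 1 is likely, and a gain of 0 to 1.0 points is more plausible than the full 1.4.

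**5. Gain for #2.** Percent change already divides by baseline, and entry restricts NRS to 6–10. With assumed residual SD 2.5, effect 1.25 points and follow-up slope on baseline from 0.2 to 1.2, power was 78.9–81.1% for the t-test and 79.5–80.4% for ANCOVA: about nil. No comparable calculation was made for #6 and #7.

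**6. What ANCOVA can lose.** With normal data and an uninformative baseline, power at 7.23 is 78.7% against 79.6% for the t-test. Under skew 1.8 with an uninformative baseline it is about 79% against 93% for Wilcoxon.

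**The case against.** The strongest reply is that the unadjusted tests are valid, that baseline already enters #3 through the change score, and that naming Welch's t-test would close the choice, match the printed interval and stay close to Table 1 with no covariate at all. Much of this stands. Welch would remove the more important half of the problem. What it leaves is the possible precision at #3, which costs only wording.

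The larger figures also rest on an assumed skew for a bounded scale. With normal data the effects are small, and SAP 1.6 makes the smaller-p-value scenario an upper bound. That is fair, and the size is stated accordingly.

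Third, the method for continuous secondaries is blacked out in Protocol 8.2.2, and SAP 2.5 sends CHW details to the Adaptive Design Plan, which is not among the documents. Either may name a test. The point is therefore limited to the wording of SAP 2.2.1 and 2.3.2. A reader might infer that the CHW input for #2 and #3 is undefined; the documents do not support that, only that the SAP does not state it.

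A reader might also infer that stratification by site (Protocol 6.3) calls for a fixed site term with sites under 10 subjects pooled, as an extension of SAP 2.10. SAP 2.10 excludes such sites from an interaction check and pools nothing. With about 140 subjects over up to 30 sites (Protocol Appendix XII), the average is 140/30 = 4.7 per site, so most subjects would land in one pooled group.

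**Conclusion.** The point holds as an open choice of test combined with some lost precision. The change should be made, but the conclusions of the trial do not depend on it. The missing rule follows from the SAP text alone. Its size is disagreement in about 5% of trials at the ODI design difference (about 13% under the assumed skew) and a worst-case size of about 0.06 (0.069 under the skew). The value of the covariate is less certain: for #3 the detectable difference falls from 7.2 to about 5.8–7.2 depending on the assumed ρ and k; it is about nil for #2 and not established for #6 and #7.

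Three stronger readings should be resisted. The unadjusted analysis is not biased. The 3:2 allocation does not by itself invalidate a pooled t-test; unequal SDs would have to accompany it, and Table 1 uses one SD per endpoint, so variance-robust errors are a safeguard and not a necessity. Finally, ANCOVA does not correct for the exclusions after randomization that define the PTE population (SAP 2.1).

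**What to change.** Before the interim analysis, state in SAP 2.2.1 and 2.3.2:

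- Secondary endpoints #2, #3, #6 and #7 are each tested by ANCOVA of the endpoint as already defined, with treatment and the corresponding baseline score in the model and standard errors that allow unequal variances (for example HC3).
- The adjusted mean difference, its 95% confidence interval and the p-value all come from this model.
- t-test and Wilcoxon results are supportive only.

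No site term is required. If one is wanted because randomization is stratified by site, specify a form that works with few subjects per site. Check that the stage-wise statistic for #2 and #3 in the Adaptive Design Plan agrees with the named test, and align the two documents if it does not.

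The cost is SAP wording and standard SAS code, with no added subjects and no changed endpoint. Two downsides should be accepted knowingly: about 1 power point lost if baseline is uninformative, and lower power than Wilcoxon if outcomes are strongly skewed. A sponsor expecting strong skew could instead name Wilcoxon now with a matching location-shift interval, which also closes the choice.
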